9.2. Setting

The information in Section 9.2 addresses the prospective DAA-PASS cohort only. Information related to the historical cohort is described in Section 9.7.9.

9.2.1. Study Population

The prospective DAA-PASS cohort will include a subset of HCV RNA positive participants in TARGET-HCC who meet screening criteria including HCV (with no prior history of DAA therapy) and newly diagnosed BCLC Stage A HCC (see Section 9.2.2). Participants will be enrolled if they fulfil the enrollment criteria (see Section 9.2.3).

Participants will be enrolled in the countries participating in TARGET-HCC which will include US, France, Germany, Italy, and Spain.

9.2.2. Screening

Participants in the prospective cohort will be screened during or before a regularly scheduled clinic visit. The following will be completed:

- Obtain signed informed consent
- Review and confirm screening inclusion/exclusion criteria

Participants who consent will enter the Screening Phase of DAA-PASS and will be identified by their unique Participant ID number from TARGET-HCC.

9.2.2.1. Screening Inclusion Criteria

Participants must meet all of the following to be eligible for participation in DAA-PASS:

Current participant in TARGET-HCC

Adults, age ≥ 18 years

First diagnosis of HCC (mixed HCC/cholangiocarcinoma may be included). Diagnosis may be histological/cytological and/or radiological.

BCLC Stage A

Underwent, undergoing, or planned to undergo therapy for HCC, with exception that transplant as prior or planned treatment for HCC is excluded.

HCV RNA positive

9.2.2.2. Screening Exclusion Criteria

Participants who meet any of the following exclusion criteria will not be eligible for participation in DAA-PASS:

- Inability to provide informed consent
- HCC-free imaging (as defined in Section 9.1.1) after treatment of initial HCC that is greater than 4 weeks prior to Screening (see Section 9.2.9 for imaging details)

- Prior liver transplantation
- Hepatitis B Virus (HBV) surface antigen positive (HBsAg)
- Previously treated with direct-acting antiviral agents (not DAA-naïve); Note that prior (peg)IFN and/or ribavirin therapy is allowed

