7.3. Purpose and rationale

DAA-PASS will investigate early recurrence of HCC in HCV-positive patients who have received successful treatment of HCC, defined as no evidence of HCC by imaging at study baseline; early recurrence will be considered recurrence within the follow up period after the first HCC-free image. DAA-PASS will utilize a prospective cohort design that estimates the risk of HCC recurrence as a time-varying function of all-oral DAA exposure. In the prospective cohort, all participants begin DAA-PASS as DAA-therapy naïve. Participants who subsequently start

DAA therapy during the study may contribute person-time regarding both the exposure to and the absence of exposure to DAA when estimating HCC recurrence risk. Thus, the DAA-treatment variable is time-varying.

DAA-PASS will benefit from prospectively enrolling participants from ongoing TARGET-HCC. DAA-PASS will incorporate the heterogeneity in clinical practice, utilizing the natural variability in DAA therapy initiation times to generate patient follow-up that includes contemporary surveillance of both DAA exposure and absence of exposure to DAA. The study includes a standardized HCC surveillance protocol.

Additionally, prospective enrollment into DAA-PASS will include collection of baseline criteria that will provide a consistent analysis of the population at risk for early HCC recurrence across the study sites. Participants will be enrolled in the study only if they have confirmation of successful treatment of HCC prior to administration of any DAA therapy. The study design allows for collection of additional potential confounding variables that could be included in the analyses.

Analyses for Secondary Objectives B and C will be conducted to estimate the risk and adjusted incidence of early HCC recurrence associated with DAA therapy exposure relative to no DAA therapy exposure after integrating data from the prospective DAA-PASS cohort with data from a historical cohort of HCV patients untreated during the follow-up period who have been successfully treated for previous HCC (from the Italian Liver Cancer Group [ITA.LI.CA] study cohort which has been identified as a source of historical cohort data). These historical cohort data will contribute person-time without DAA exposure when estimating HCC recurrence risk.

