9.2.3. Enrollment/Baseline

Successful treatment of HCC must be confirmed by imaging for enrollment (see Section 9.2.9). Additionally, it must be confirmed that the participant meets the Enrollment criteria. Once confirmed, the participant will be enrolled and the date of the first HCC-free image will be considered Enrollment/Baseline for DAA-PASS.

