9.2.3.1. Enrollment Inclusion Criteria

Participants must meet all of the following to be enrolled in DAA-PASS:

Continued participation in TARGET-HCC

No recurrence or progression of initial HCC beyond BCLC Stage A prior to Enrollment/Baseline

HCC-free imaging (as defined in Section 9.1.1) at Enrollment/Baseline (see Section 9.2.9 for imaging details; participants may remain in Screening until an HCC -free image is obtained)

Remains DAA-naïve (prior therapy with (peg)IFN and/or ribavirin is allowed)

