9.2.8. DAA-PASS Schedule of Events

The schedule of events is summarized in Table 2.

Table 2. Prospective DAA-PASS Cohort Events Schedule

Assessment	Screening	Enrollment / Baseline	Follow-up	End of DAA-PASS
			Imaging Months 3, 6, 9, 12, 18, and 24 ¹	
Informed consent ^{2,3}	X			
Review of Screening inclusion/exclusion criteria	X ^{4, 7}			
Review of Enrollment inclusion/exclusion criteria		X ⁴		
Imaging ¹		X	X	
Confirm successful treatment of HCC (HCC-free image; see Section 9.1.1 and Section 9.2.9)		X ⁵		
Confirm no HCC recurrence			X	
DAA therapy exposure ⁶		X	X	
Final disposition				X

1 Per standard of care (See Section 9.2.9).

2 Study procedures will be completed during or before regularly scheduled clinic visits.

3 Participant can withdraw her/his consent at any time after she/he is enrolled in the study.

4 Participants who do not meet criteria are Screen Failures.

5 Participants who do not have an HCC-free image may remain in Screening for additional initial HCC-treatment intervention(s) and subsequent imaging until HCC-free on imaging as appropriate per standard of care.

6 DAA therapy can be initiated anytime from Enrollment/Baseline through Follow-up.

7 Participants are allowed to enroll using an HCC-free image obtained up to 4 weeks prior to signing DAA-PASS consent.

NOTE: As all participants enrolled in DAA-PASS remain enrolled in TARGET-HCC, the data collected as part of TARGET-HCC up to completion or discontinuation of DAA-PASS will also be available and therefore are not specified in 2:

- All data available in the medical record up to 3 years prior to enrollment in TARGET-HCC (e.g., clinic notes/encounters and telephone contact notes/reports, laboratory reports, medical history [including HCV and other comorbid diseases] medication lists, hospitalization records, radiographic/imaging reports/results, biopsy reports/results, diagnostic procedures such as liver biopsy reports and endoscopic examinations, all prior clinical details specific to screening methods, diagnostic evaluation, and HCC treatment intervention).
- Any/all details regarding prior and current HCV and HBV including: treatments, assessment results, and responses.
- Any/all investigator-assessed HCC disease staging/scoring and responses to HCC treatment interventions.

- Any/all investigator-assessed liver disease staging/scoring.

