9.7.3. DAA Exposure as Time-Varying Exposure

Individual participants in the prospective DAA-PASS cohort can contribute person-time to both DAA exposure and no DAA exposure. DAA exposure is a function of time. The no DAA exposure starts at the enrollment/baseline image (Index Date; i.e., successful treatment of HCC) and continues until the participant has an event (i.e., HCC recurrence), initiates DAA therapy, completes the study without initiating DAA therapy, or is otherwise censored. The DAA exposure starts at the first date a DAA is initiated and continues until the participant has an event, completes the study, or is otherwise censored. Participants are censored in whichever exposure type they are in (no DAA exposure or DAA exposure) if they receive IFN treatment, a liver transplant, die, withdraw from the study, or are otherwise removed or lost to follow-up while enrolled in DAA-PASS. Participants that receive DAA therapy starting on the date of Enrollment/Baseline only contribute person-time to DAA exposure and participants that never receive DAA therapy only contribute person-time to the no DAA therapy exposure person-time. The completion of the study is defined by obtaining imaging corresponding to the 24-month follow-up assessment. Note that participants who received a liver transplant while enrolled in DAA-PASS will continue to be followed up to 24 months from Enrollment/Baseline.

Additional information on DAA therapy will be collected including, as available, the DAA prescribed, duration of dosing and planned duration, and SVR response. These will be summarized descriptively.

9.7.4. Coding Convention for HCC Recurrence and DAA as Time-Varying Exposure for the Primary Analysis

This section provides additional details on the coding of the HCC recurrence endpoint for analysis. The primary model of time of onset is based on interval-censoring as outlined in Section 9.7.6.1. The intervals between imaging evaluations are not required to have a fixed length and a participant with a missed visit would simply experience an extended interval -- assuming they have a later follow-up assessment. For the analysis, individuals will have a record of an event or not corresponding to each available interval of no DAA exposure or DAA exposure. The table below provides some examples of participant data where t_{i0} is baseline and t_{ij} for $j = 1$ to n_i represent sequential imaging assessment times for the i^{th} participant:

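### DAA-naïvety is judged at Screening, up to 4 weeks after the index image, so patients who start DAA between image and consent are excluded by exposure after time zero

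*Protocol*

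**What the plan says.** **Time zero.** Section 9.1.1 defines Enrollment/Baseline and the index date as the first HCC-free image. Section 9.2.3 repeats it: "the date of the first HCC-free image will be considered Enrollment/Baseline for DAA-PASS". Section 4.6 takes model covariates up to that image.

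**Gap before consent.** Table 2, footnote 7 (Section 9.2.8): "Participants are allowed to enroll using an HCC-free image obtained up to 4 weeks prior to signing DAA-PASS consent". Section 9.2.2.2 sets the matching limit by excluding an HCC-free image "that is greater than 4 weeks prior to Screening".

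**DAA-naïve rules.** Section 9.2.2.2 excludes anyone "Previously treated with direct-acting antiviral agents", as a Screening criterion and with no exception for a start after the index image. Section 9.2.3.1 adds "Remains DAA-naïve (prior therapy with (peg)IFN and/or ribavirin is allowed", without saying on which date this is judged.

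**Permitted DAA start.** Table 2, footnote 6: "DAA therapy can be initiated anytime from Enrollment/Baseline through Follow-up". Section 9.3 likewise permits a start at any time after Enrollment/Baseline. Section 7.3 states: "Participants will be enrolled in the study only if they have confirmation of successful treatment of HCC prior to administration of any DAA therapy". On coding, Section 9.7.3 says "Participants that receive DAA therapy starting on the date of Enrollment/Baseline only contribute person-time to DAA exposure", and Table 3 treats any start in the first imaging interval as exposed from the beginning of follow-up.

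**The concern.** Follow-up starts at the image, but prior DAA use is judged at Screening, when consent is obtained. When the image comes first, whatever happens between the two dates lies after time zero and still decides whether the patient enters. The event that decides it is the exposure under study, so the rule removes exposed patients only.

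Those removed are the earliest starters. They belong to the subgroup that starts DAA within 6 months (Section 9.7.2), and Section 9.7.6.3 codes a separate effect for that group. The expected cohort is 40 to 70, and Section 4.8 says no upper confidence bound is calculable at 50 or fewer, so a few exposed patients are worth keeping. Sites may also apply an undated criterion differently.

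**Working it through.** The plan gives no figure on this point to reproduce. The check is a timeline, followed by a rough size.

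**Timeline.** Take an HCC-free image on day 0, DAA start on day 10 and consent on day 20.

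| Place | Result for this patient |
|---|---|
| 9.1.1, 9.2.3 | Time zero is day 0 |
| Table 2, footnote 7 | Image is 20 days before consent: allowed |
| 7.3 | HCC-free confirmation precedes DAA: condition met |
| Table 2, footnote 6; 9.3 | DAA starts after Enrollment/Baseline: allowed |
| Table 3 | Would be coded exposed from the beginning of follow-up |
| 9.2.2.2 | DAA before Screening: excluded |
| 9.2.3.1 | Met if judged on day 0, failed if judged when enrolment is confirmed |

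Footnotes 6 and 7 of the same table cannot both be honoured for this patient under 9.2.2.2.

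**Size.** Inputs: 42% of recurrence-free participants treated by 6 months (Section 9.5.1); a gap L of up to 28 days (footnote 7); 40 to 70 participants (Section 4.8). Six months is taken as 365.25/2 = 182.6 days. The shape of uptake within those months is an assumption, so two are shown.

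- Linear: 0.42 × L/182.6. At L = 28: 0.42 × 28/182.6 = 6.4%.
- Constant hazard: 1 − 0.58^(L/182.6). At L = 28: 1 − 0.58^0.153 = 8.0%.

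| Gap L | Linear | Constant hazard |
|---|---|---|
| 7 days | 1.6% | 2.1% |
| 14 days | 3.2% | 4.1% |
| 21 days | 4.8% | 6.1% |
| 28 days | 6.4% | 8.0% |

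If every patient entered image-first with the full gap:

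- per 40: 40 × 6.4% = 2.6 to 40 × 8.0% = 3.2 patients;
- per 70: 70 × 6.4% = 4.5 to 70 × 8.0% = 5.6 patients.

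If half entered image-first with a 14-day gap (assumption), the loss is 20 × 3.2% = 0.6 to 35 × 4.1% = 1.4 patients. If every patient consented before the image, the Screening exclusion would remove nobody for a start after the image.

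One assumption would raise these figures. If the whole 42% started within 3 months, the 28-day share would be about 13% to 15%. Section 9.5.1 gives no sign of this: its uptake quickens after 6 months, with a further 44% out of the remaining 58% (44/58 = 76%) starting by 12 months.

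**The case against.** **The cohort is simply meant to be DAA-naïve at entry.** Section 7.3 also says everyone begins the study DAA-naïve, Section 9.1.1 says nobody is exposed at Enrollment, and Section 9.2.4.1 places the DAA decision after enrolment. The condition quoted from 7.3 is necessary rather than sufficient, and 9.7.3 and Table 3 are coding rules for people already in the study. This narrows the textual conflict to footnotes 6 and 7 of Table 2, with 9.3, against 9.2.2.2. It does not remove it, because the protocol defines Enrollment as the image date. Even if naïvety at consent is intended, entry still depends on exposure after time zero.

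**Stronger readings that a reader might infer:**

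- *A guaranteed DAA-free stretch biases the hazard ratio.* A gap of 28 days or less lies inside the first imaging interval of about 3 months, and Table 3 codes that whole interval as exposed for any start in it. What remains is the loss of the early starters themselves.
- *A consent-first patient with the same course is clearly kept.* The Screening exclusion does not catch that patient, but the undated 9.2.3.1 might.
- *The rule removes the pattern behind the safety signal.* For the uncontrolled 58-patient study, Section 7.2 gives the time from DAA start to recurrence and the length of follow-up. It does not give the time from HCC treatment to DAA.
- *This explains the poor enrolment.* Section 9.5.1 attributes that to HCV being treated before HCC.

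**It may be too late.** Data collection ends in 2Q2021, and the annexed ENCePP checklist carries a date of 22 November 2021. Consent also precedes the criteria review, so patients already on DAA may never have been logged as screen failures. Both points limit what a change can recover. The selection would still need to be stated when results are reported.

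**Conclusion.** The point holds for image-first patients: a stated eligibility rule selects on exposure after the protocol's own time zero, and it conflicts with the rule that DAA may start from Enrollment/Baseline. It takes some of the earliest starters out of the within-6-months subgroup.

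The size is modest. At the full 28-day gap the loss is 6.4% to 8.0% of image-first patients, at most about 3 to 6 per 40 to 70 if all entered that way. The true figure is probably far lower. This rests on the 42% uptake figure and on the two assumed uptake shapes; the document gives neither the image-first share nor the distribution of the gap. The effect on the hazard ratio is probably small and cannot be quantified from the document. The correction is worth making because it is cheap and the cohort is very small, not because it threatens the primary estimate.

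**What to change.** - In 9.2.2.2 and 9.2.3.1, define DAA-naïve as no DAA before the date of the first HCC-free image.
- Tie the HCV RNA criterion in 9.2.2.1 to the same date. Otherwise it would still be judged at Screening, after DAA may have started.
- Code a DAA start between image and consent by the existing Table 3 interval convention. Delayed entry at consent is not a good alternative: no image is scheduled at consent, so it would split an interval-censored period at a point where recurrence status is unknown.
- Check screen failures recorded as not DAA-naïve against the new definition. Section 9.2.5 says the reasons are collected and that these patients stay in TARGET-HCC. Given the logging limit above, the count is a minimum.
- If the criteria can no longer be changed, state the selection and that count in the report.

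The cost is a short amendment to three criteria and one review of existing records. The downside is that a few participants would already have started DAA at consent, so the statements in 7.3 and 9.1.1 about entering DAA-naïve need to refer to the index date. The change concerns eligibility dating only and sets no treatment rule.

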9.2.3. Enrollment/Baseline

Successful treatment of HCC must be confirmed by imaging for enrollment (see Section 9.2.9). Additionally, it must be confirmed that the participant meets the Enrollment criteria. Once confirmed, the participant will be enrolled and the date of the first HCC-free image will be considered Enrollment/Baseline for DAA-PASS.

9.2.3.1. Enrollment Inclusion Criteria

Participants must meet all of the following to be enrolled in DAA-PASS:

Continued participation in TARGET-HCC

No recurrence or progression of initial HCC beyond BCLC Stage A prior to Enrollment/Baseline

HCC-free imaging (as defined in Section 9.1.1) at Enrollment/Baseline (see Section 9.2.9 for imaging details; participants may remain in Screening until an HCC -free image is obtained)

Remains DAA-naïve (prior therapy with (peg)IFN and/or ribavirin is allowed)

9.2.3.2. Enrollment Exclusion Criteria

Participants who meet the following exclusion criterion will not be enrolled in DAA-PASS:

- Liver transplantation since Screening

9.2.4. Follow-up

The Follow-up period will continue for up to 24 months from Enrollment/Baseline for all participants. Imaging will be performed per standard of care^{10,11}, as follows (see Table 2):

- Every 3 months for the first 12 months after Enrollment/Baseline
- At 18 and 24 months after Enrollment/Baseline

9.2.4.1. DAA Therapy

Once enrolled in the study, the decision to treat participants with DAA therapy for HCV will be made per standard of care and at the discretion of the treating physician. For all participants who receive DAA therapy after enrollment in DAA-PASS, details regarding the DAA therapy and virologic response will be recorded.

9.2.5. Screen Failures

Participants will be considered Screen Failures if they do not meet the Screening or Enrollment Inclusion criteria and/or if they meet the Screening or Enrollment Exclusion criteria (see

Section 9.2.2 and Section 9.2.3). Details regarding reasons for Screen Failure will be collected in the DAA-PASS database. Participants who are Screen Failures will remain enrolled in TARGET-HCC.

9.2.6. Completion and Discontinuation of Participants

A participant will be considered as complete in the DAA-PASS, if they meet any of the following:

- Complete up to 24 months of Follow-up after Enrollment/Baseline
- Death (due to any cause) during Follow-up while still enrolled in DAA-PASS

Participants will be discontinued from DAA-PASS for the following reasons:

- Participant choice, withdrawal of consent
- Lost to follow-up
- Administrative (e.g., site closure, Sponsor termination of the study, study completion as defined in Section 9.2.7)

Although participation in DAA-PASS for each participant will end after Screen Failure (at Screening or Enrollment/Baseline), Completion, or Premature Discontinuation, living participants will remain enrolled in TARGET-HCC. For clarity, any subsequent data collected after participation in DAA-PASS will only be available as part of TARGET-HCC.

If a participant chooses to withdraw from TARGET-HCC, they will consequently also be choosing to withdraw from DAA-PASS.

If a participant chooses to withdraw from DAA-PASS, all data collected up to the point of withdrawal will remain for use in the study database, unless otherwise prohibited by local regulations, but no further data may be collected. A request to withdraw must be documented in the participant's medical record by the study site personnel to be consistent with privacy guidelines and regulations.

For participants who die during their participation in DAA-PASS, it will be the responsibility of the Investigator to assign a cause of death based upon available clinical information, hospital records, and/or death certificate; the relevant death information will be included in the database. Site staff may also search publicly available sources for any information regarding death of a participant and may submit that information for entry into the database after the discontinuation date.

9.2.7. Completion or Discontinuation of DAA-PASS

DAA-PASS will be considered complete after the last enrolled participant completes or discontinues from the DAA-PASS (as described in Section 9.2.6).

Additionally, the Sponsor may terminate DAA-PASS after consultation with the PRAC.

9.2.8. DAA-PASS Schedule of Events

The schedule of events is summarized in Table 2.

Table 2. Prospective DAA-PASS Cohort Events Schedule

Assessment	Screening	Enrollment / Baseline	Follow-up	End of DAA-PASS
			Imaging Months 3, 6, 9, 12, 18, and 24 ¹	
Informed consent ^{2,3}	X			
Review of Screening inclusion/exclusion criteria	X ^{4, 7}			
Review of Enrollment inclusion/exclusion criteria		X ⁴		
Imaging ¹		X	X	
Confirm successful treatment of HCC (HCC-free image; see Section 9.1.1 and Section 9.2.9)		X ⁵		
Confirm no HCC recurrence			X	
DAA therapy exposure ⁶		X	X	
Final disposition				X

1 Per standard of care (See Section 9.2.9).

2 Study procedures will be completed during or before regularly scheduled clinic visits.

3 Participant can withdraw her/his consent at any time after she/he is enrolled in the study.

4 Participants who do not meet criteria are Screen Failures.

5 Participants who do not have an HCC-free image may remain in Screening for additional initial HCC-treatment intervention(s) and subsequent imaging until HCC-free on imaging as appropriate per standard of care.

6 DAA therapy can be initiated anytime from Enrollment/Baseline through Follow-up.

7 Participants are allowed to enroll using an HCC-free image obtained up to 4 weeks prior to signing DAA-PASS consent.

NOTE: As all participants enrolled in DAA-PASS remain enrolled in TARGET-HCC, the data collected as part of TARGET-HCC up to completion or discontinuation of DAA-PASS will also be available and therefore are not specified in 2:

- All data available in the medical record up to 3 years prior to enrollment in TARGET-HCC (e.g., clinic notes/encounters and telephone contact notes/reports, laboratory reports, medical history [including HCV and other comorbid diseases] medication lists, hospitalization records, radiographic/imaging reports/results, biopsy reports/results, diagnostic procedures such as liver biopsy reports and endoscopic examinations, all prior clinical details specific to screening methods, diagnostic evaluation, and HCC treatment intervention).
- Any/all details regarding prior and current HCV and HBV including: treatments, assessment results, and responses.
- Any/all investigator-assessed HCC disease staging/scoring and responses to HCC treatment interventions.

- Any/all investigator-assessed liver disease staging/scoring.
- All prospective data available in the medical record from enrollment in TARGET-HCC. Data are collected every 3 months for the first year and every 6 months for subsequent years, unless requested more frequently for planned analyses.
- Any adverse events (AEs; see Section 11.1.1), including serious adverse events (SAEs; see Section 11.3).

